9.3.3 Sensitivity and Supplementary Analyses of the Primary Efficacy Endpoint

As a sensitivity analysis, a 2-sided 95% confidence interval using the Wilson-Newcombe method will be presented.

In addition, the following sensitivity analyses with respect to missing data handling approaches will be conducted to explore the robustness of the primary efficacy analysis results:

- Observed data without imputation: The comparison between AGN-190584 and vehicle for the primary efficacy endpoint will be made using the Pearson's chi-square test based on observed data without imputation.
- Last observation carried forward (LOCF): Missing data for the primary efficacy endpoint at Day 14, Hour 9 will be imputed using a time matched LOCF, and the comparison between AGN-190584 and Vehicle for the primary efficacy endpoint will be conducted based on the data after imputation.

9.4 Secondary Efficacy Endpoints and Analyses

9.4.1 Key Secondary Efficacy Endpoint

Proportion of subjects gaining 3 lines or more in photopic, high-contrast, binocular DCNVA with no more than 5-letter loss in photopic CDVA with the same refractive correction at Day 14, Hour 9 (3 hours after the second dose).

9.4.2 Main Analyses of Key Secondary Efficacy Endpoint

The attributes of the estimand corresponding to the key secondary efficacy endpoint are summarized in Table 2.

Table 2. Summary of the Estimand Attributes of the Key Secondary Efficacy Endpoint

Estimand Label	Attributes of the Estimand				
	Treatment	Endpoint	Population	Handling of Intercurrent Events	Statistical Summary
Estimand for the key secondary endpoint	AGN-190584 or vehicle	The proportion of subjects gaining 3 lines or more in photopic, high-contrast, binocular DCNVA with no more than 5-letter loss in photopic CDVA with the same refractive correction at Day 14, Hour 9 (3 hours after the second dose)	ITT	The composite strategy will be applied to handle the intercurrent events. Missing data will be regarded as a non-responder for the endpoint.	The difference and the corresponding 95% confidence interval in the proportion of subjects gaining 3 lines or more in photopic, high-contrast, binocular DCNVA with no more than 5-letter loss in photopic CDVA with the same refractive correction at Day 14, Hour 9 between AGN-190584 and vehicle.

DCNVA = distance-corrected near visual acuity; CDVA = corrected distance visual acuity; ITT = intent to treat

As presented in the estimand for the key secondary efficacy endpoint in Table 2, the composite strategy will be used to handle the intercurrent events. Subjects with intercurrent events prior to Day 14, Hour 9 will be considered as non-responders for the key secondary efficacy endpoint. Subjects who have missing data for the key secondary efficacy endpoint will be categorized as non-responders in the primary analysis.

The comparison of the proportions between AGN-190584 and vehicle will be made using the Pearson's chi-square test. The treatment difference will be provided with a 2-sided 95% CI using the normal approximation based on the pooled variance without continuity correction.

If the proportions of subjects with reported IEs are considered unbalanced between the treatment groups and are higher in the vehicle group than in the AGN-190584 group, the subjects with IEs will not be considered as nonresponders for the key secondary efficacy analysis.

9.4.3 Sensitivity and Supplementary Analyses for Key Secondary Efficacy Endpoint

Similar as for the primary efficacy endpoint, a 2-sided 95% confidence interval using Wilson-Newcombe method will be presented for the key secondary efficacy endpoint.

In addition, the following sensitivity analyses with respect to missing data handling approaches will be conducted to explore the robustness of the key secondary efficacy analysis results:

- Observed data without imputation: The comparison between AGN-190584 and vehicle for the key secondary efficacy endpoint will be made using the Pearson's chi-square test based on observed data without imputation.
- Last observation carried forward (LOCF): Missing data for the key secondary efficacy endpoint at Day 14, Hour 9 will be imputed using a time matched LOCF, and the comparison between AGN-190584 and vehicle for the key secondary efficacy endpoint will be conducted based on the data after imputation.

9.4.4 Supportive Secondary Efficacy Endpoints and Analyses

Supportive Secondary Endpoints:

1. Proportion of subjects gaining 2 lines or more in mesopic, high-contrast, binocular DCNVA with no more than 5-letter loss in mesopic CDVA with the same refractive correction at Day 14, Hour 9 (3 hours after the second dose)
2. Proportion of subjects achieving 20/40 or better in mesopic, high-contrast, binocular DCNVA with no more than 5-letter loss in mesopic CDVA with the same refractive correction at Day 14, Hour 9 (3 hours after the second dose)

The same analysis method as described in Section 9.3.2 for the primary efficacy endpoint will be applied for the above supportive secondary endpoints. The comparison of the proportions between AGN-190584 and vehicle will be made using the Pearson's chi-square test. The treatment difference will be provided with a 2-sided 95% CI using the normal approximation based on the pooled variance without continuity correction.

9.5 Additional Efficacy Endpoints and Analyses

The additional efficacy endpoints are:

1. Change from baseline in mesopic Near Vision Presbyopia Task-based Questionnaire (NVPTQ) Performance score at Day 14, Hour 9 (3 hours after the second dose)
2. Change from baseline in Presbyopia Impact and Coping Questionnaire (PICQ) Coping score at Day 14, Hour 3
3. Change from baseline in Visual Function Assessment application (VFA app) at Day 14, Hour 9 (3 hours after the second dose):
 - Change from baseline in average number of blinks per minute
 - Change from baseline in median working distance (centimeters)
 - Change from baseline in median magnification level (%) from the original size

- Change from baseline in reading speed (words per minute)
- Change from baseline in median contrast level (%) based on the original value

The PRO scoring algorithms for the NVPTQ, PICQ, and VFA app are provided in Appendix A.

The additional efficacy endpoints will be analyzed using an ANCOVA model that includes treatment, age group, baseline DCNVA severity group, iris color group, and emmetrope status as factors as well as corresponding baseline PRO score as a covariate.

The same analysis will be applied for these PRO scores at other visits/timepoints.

Additionally, for the PRO domain mesopic NVPTQ Performance score at Day 14 Hour 9 and the PRO domain PICQ Coping score at Day 14 Hour 3, the cumulative distribution function (CDF) curves representing the cumulative proportion of subjects with any particular level of change from baseline in a PRO domain will be presented by treatment group.

9.6 Exploratory Efficacy Endpoints and Analyses

Exploratory efficacy endpoints are not defined in the protocol and will be included for exploratory analyses:

- Change from baseline in mesopic near pupil diameter
- Change from baseline in mesopic distance pupil diameter
- Change from baseline in photopic near pupil diameter
- Change from baseline in photopic distance pupil diameter

Descriptive statistics for pupil diameter (mesopic near, mesopic distance, photopic near and photopic distance) and changes from baseline values at each assessment timepoint will be presented by treatment group and by eye (dominant and non-dominant).

Additionally, similar analysis methods as described for primary (Section 9.3.2) and secondary efficacy endpoints (Section 9.4.2) will be used for the following exploratory efficacy endpoints based on observed data.

- The proportion of subjects gaining 3 lines or more in mesopic, high-contrast, binocular DCNVA with no more than 5-letter loss in mesopic CDVA with the same refractive correction at all visits/timepoints other than Day 14, Hour 9 (3 hours after the second dose)
- The proportion of subjects gaining 3 lines or more in photopic, high-contrast, binocular DCNVA with no more than 5-letter loss in photopic CDVA with the same refractive correction at all visits/timepoints other than Day 14, Hour 9 (3 hours after the second dose)
- The proportion of subjects gaining 2 lines or more in mesopic, high-contrast, binocular DCNVA with no more than 5-letter loss in mesopic CDVA with the same refractive correction at all visits/timepoints
- The proportion of subjects achieving 20/40 or better in mesopic, high-contrast, binocular DCNVA with no more than 5-letter loss in mesopic CDVA with the same refractive correction at all visits/timepoints

9.7 Efficacy Subgroup Analyses

Subgroup analyses will be conducted for the primary and key secondary endpoints for the following subgroups:

- Age group (≤ 50 , > 50 years)
- Sex (male, female)
- Race (white, black or African American, Asian, American Indian or Alaska Native, Native Hawaiian or other Pacific Islander, and multiple.)
- Ethnicity (Hispanic or Latino, not Hispanic or Latino)
- Baseline binocular DCNVA (20/63 or better, worse than 20/63)
- Iris color (brown, non-brown)
- Emmetropic status (emmetropes, non-emmetropes)

Descriptive summary statistics and 95% confidence intervals will be provided; no statistical hypothesis test will be performed. For any subgroup with < 10 subjects in a treatment group, only descriptive summary statistics will be provided.

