2.3 Treatment Assignment and Blinding

Subjects will be randomized in a 1:1 ratio to receive either AGN-190584 or vehicle dosed twice daily, in each eye, for 14 days.

Randomization will be further stratified by the following stratification factors:

- Age group: ≤ 50 years and > 50 years
- Baseline binocular mesopic DCNVA severity: 20/63 or better, and worse than 20/63; with a maximum of 50% enrolled subjects with baseline binocular mesopic DCNVA of 20/63 or better
- Iris color: brown and nonbrown
- Emmetropie status: emmetrope and nonemmetrope; with a maximum of 25% enrolled subjects with non-emmetrope. A subject will be considered as emmetrope if both eyes of the subject satisfy the 2 criteria based on best cycloplegic distance correction: 1) -0.5D to +0.75D in sphere, inclusively; and 2) ≤ 0.75D in Cylinder.

All AbbVie personnel with direct oversight of the conduct and management of the study (with the exception of the AbbVie Drug Supply Management Team), the investigator, study site personnel, and the subject will remain masked to each subject's treatment throughout the study. To maintain the masking, the AGN-190584 and vehicle containers provided for the study will be identical in appearance. The IRT will provide access to unmasking subject treatment information in the case of a medical emergency.

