2.4 Sample Size Determination

The sample size calculation was considered for the primary efficacy endpoint, proportion of subjects gaining 3 lines or more in mesopic, high-contrast, binocular DCNVA with no more than 5-letter loss in mesopic CDVA with the same refractive correction at Day 14, Hour 9 (3 hours after the second dose).

Assuming a responder rate of 25% in the AGN-190584 group and 7% in the vehicle group, and a 5% dropout rate, a sample size of 100 subjects per study treatment group will

provide greater than 90% power using chi-square testing at a 2-sided significance level of 5%.

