9.0 Efficacy Analyses

9.1 General Considerations

All efficacy analyses will be conducted for all efficacy endpoints in the ITT population at the end of the study and after the database has been locked. All tests will be 2-sided at an alpha level of 0.05. All confidence intervals (CIs) will be at least 2-sided 95% confidence.

Unless otherwise specified, the comparison of the proportions between AGN-190584 and vehicle will be made using the Pearson's chi-square test, and the treatment difference will be provided with a 2-sided 95% CI using the normal approximation based on the pooled variance without continuity correction.

Continuous variables will be analyzed using an analysis of covariance (ANCOVA) model that includes treatment, age group, baseline DCNVA severity group, iris color group, and emmetrope status as factors as well as corresponding baseline value as a covariate.

Unless otherwise specified, any mis-stratified subject will be analyzed based on the actual stratum the subject should have been randomized.

"Baseline" refers to the last non-missing observation before the first administration of study treatment or randomization if no study treatment is given. The change from baseline values will be computed as the postbaseline value minus the baseline value.

For descriptive analyses:

- Categorical variables will be summarized with the number and percentage of subjects; unless otherwise stated, percentages will be calculated based on the number of non-missing observations.
- Continuous variables will be summarized with descriptive statistics (number of nonmissing observations, mean and standard deviation, median, 1st and 3rd quartiles, minimum, and maximum).

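### SAP 9.7 names no method for subgroup confidence intervals; the default pooled normal interval can be too narrow, or exactly 0 to 0, when a small subgroup has almost no responders (minor)

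*SAP*

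**What the plan says.** SAP 9.7 covers the primary and key secondary endpoints by age group, sex, race, ethnicity, baseline DCNVA, iris color and emmetropic status. On output it says: "Descriptive summary statistics and 95% confidence intervals will be provided; no statistical hypothesis test will be performed". The only safeguard for small cells is: "For any subgroup with < 10 subjects in a treatment group, only descriptive summary statistics will be provided". An interval is therefore printed when both arms have at least 10 subjects. No interval method is named.

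SAP 9.1 supplies the general rule for proportions. It opens "Unless otherwise specified, the comparison of the proportions between AGN-190584 and vehicle will be made using the Pearson's chi-square test" and continues that "the treatment difference will be provided with a 2-sided 95% CI using the normal approximation based on the pooled variance without continuity correction". Section 9.7 specifies nothing different.

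A second method appears in SAP 9.3.3: "As a sensitivity analysis, a 2-sided 95% confidence interval using the Wilson-Newcombe method will be presented". SAP 9.4.3 does the same for the key secondary endpoint. Both concern the full-trial comparison, not subgroups.

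The only responder rates in either document are in the sample size sections (SAP 2.4, Protocol 7.8): "Assuming a responder rate of 25% in the AGN-190584 group and 7% in the vehicle group". They are for the mesopic primary endpoint in the whole trial.

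**The concern.** A normal approximation for a difference in proportions depends on the number of responders, whereas the 9.7 cut-off looks only at the number of subjects. At the plan's rates, 10 subjects per arm means 2.5 expected responders on active and 0.7 on vehicle. Counting missing data and intercurrent events as nonresponse (SAP 8.0 and 9.2) lowers this further.

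Because no subgroup tests are planned, these intervals are the only inferential subgroup output. A printed difference of 0 with limits 0 and 0, based on 20 subjects, would state complete certainty where there is almost no information.

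**Working it through.** **Inputs.** From the documents: 25% vs 7%, 100 per arm, 5% dropout (SAP 2.4); 2-sided 5% level (SAP 9.1); 1:1 allocation and the nonemmetrope cap (SAP 2.3); the cut-off of 10 (SAP 9.7). Assumed: 15% vs 3% and 10% vs 2%, to show what happens if a subgroup or the photopic endpoint responds less often; equal arms within a subgroup.

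**The plan's own figure.** Power is Φ[(0.18√n − 1.96√(2·0.16·0.84)) / √(0.25·0.75 + 0.07·0.93)]. At n = 100 this is Φ[(1.800 − 1.016)/0.5026] = Φ(1.56) = 94.1%; at n = 95, after dropout, 92.9%. The stated power above 90% is reproduced.

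**Interval formulas.** With x1 and x2 responders out of n per arm, d = (x1 − x2)/n and p̄ = (x1 + x2)/(2n), the default interval is d ± 1.96√(2p̄(1 − p̄)/n). Wilson-Newcombe takes the Wilson limits (l, u) of each arm and gives d − √((p1 − l1)² + (u2 − p2)²) to d + √((u1 − p1)² + (p2 − l2)²).

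**Single outcomes at 10 per arm.**
- 0 vs 0: p̄ = 0, so the default is 0 to 0. The Wilson upper limit is 1.96²/(10 + 1.96²) = 0.278, so Wilson-Newcombe gives −0.278 to 0.278.
- 1 vs 0: p̄ = 0.05, half-width 1.96√(2·0.05·0.95/10) = 0.191, default −0.091 to 0.291. Wilson-Newcombe gives −0.189 to 0.404. The width ratio is 0.64.
- The ratio is 0.85 for 2 vs 0, 0.98 for 3 vs 0, 1.04 for 3 vs 1 and 1.18 for 5 vs 1.

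Marked narrowing at this size is thus confined to 0 or 1 responders in total.

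**Chance of zero width.** This is ((1 − p1)(1 − p2))^n; the all-responder case is negligible. At 10 per arm: (0.75·0.93)^10 = 2.7%; (0.85·0.97)^10 = 14.5%; (0.90·0.98)^10 = 28.5%. If both plan rates are multiplied by 0.95 for dropout counted as nonresponse, the first becomes (0.7625·0.9335)^10 = 3.3%. The chance of at most one responder in total at plan rates is 2.7% + 9.1% + 2.1% = 13.9%.

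**Coverage.** All pairs (x1, x2) of two independent binomials were enumerated, and the probabilities of pairs whose interval contains the true difference were summed.

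| Per arm | Rates | Default coverage | Zero width | Wilson-Newcombe coverage |
|---|---|---|---|---|
| 10 | 25% vs 7% | 92.9% | 2.7% | 97.6% |
| 10 | 15% vs 3% (assumed) | 79.6% | 14.5% | 99.2% |
| 10 | 10% vs 2% (assumed) | 70.8% | 28.5% | 99.8% |
| 15 | 25% vs 7% | 93.2% | 0.4% | 97.5% |
| 15 | 15% vs 3% (assumed) | 90.8% | 5.5% | 99.1% |
| 15 | 10% vs 2% (assumed) | 79.2% | 15.2% | 99.8% |
| 25 | 25% vs 7% | 95.3% | 0.0% | 95.5% |
| 25 | 15% vs 3% (assumed) | 90.1% | 0.8% | 97.4% |
| 25 | 10% vs 2% (assumed) | 92.0% | 4.3% | 98.7% |

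At plan rates, coverage is also 95.4% at 12 per arm and 95.2% at 20. It moves unevenly because the counts are discrete; 17 per arm gives 92.3%. Mean width at 10 per arm is 0.607 for the default and 0.645 for Wilson-Newcombe, about 6% less.

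Where coverage is poor, zero-width intervals are the main cause. At 10 per arm and 10% vs 2%, the shortfall from 100% is 29.2 points, of which 28.5 are zero-width outcomes.

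Unpooling the variance does not help. At 10 per arm the unpooled normal interval covers 89.9%, 79.5% and 69.9% at the three rate pairs. The problem is sparse responders, not the choice of variance.

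**The case against.** The strongest reply is that the plan's own rates show little harm. Coverage is about 2 points low at the cut-off and mostly within 2 points of nominal above it. With several responders the default interval is as wide as Wilson-Newcombe or wider. This stands. A reader might infer that subgroup intervals are far too narrow in general, and the documents do not support that. The figures of 71% to 80% need rates well below plan together with 10 to 15 per arm, and neither document gives a subgroup rate, a photopic rate or a race or ethnicity count.

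A reader might also point to nonemmetropes, enrolled "with a maximum of 25% enrolled subjects with non-emmetrope". That is at most about 50 of 200 subjects, or 25 per arm. At plan rates and that size, coverage is 95.3% and zero width practically impossible, so this subgroup does not show the problem unless it enrolls well below the cap or responds less often. Nor does an empty vehicle arm alone (48% chance at 10 per arm and plan rates) collapse the interval, because responders on active enter the pooled variance.

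A 0-to-0 interval would appear beside descriptive counts such as 0/10 and 0/10, so many readers would discount it. That limits the harm, but is no reason to print it.

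Finally, 9.7 does not say whether its intervals are for the difference or for each arm's proportion, and the 9.1 default covers only the difference. If each arm's proportion is meant, no method is given. Either way 9.7 needs a sentence.

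**Conclusion.** The point holds as a minor one. SAP 9.7 leaves the method to the 9.1 default, and its cut-off does not guard against having almost no responders. Followed as written, the plan can print an interval of zero width.

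At the only rates the documents give, the cost is small: 92.9% coverage and a 2.7% chance of zero width at the cut-off. It grows to 79.6% and 70.8% coverage at 10 per arm under the assumed lower rates. These figures rest on independent binomial outcomes, equal arms within the subgroup, and 9.7 intervals that are for the treatment difference.

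A reader might infer that the trial's conclusions are at risk. They are not: the subgroup intervals are descriptive, lie outside the fixed sequence H1 to H4 in SAP 13.0, and affect neither the type I error nor the primary result.

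**What to change.** In SAP 9.7, state that subgroup 95% confidence intervals for the treatment difference use the Wilson-Newcombe method of 9.3.3 and 9.4.3 in place of the 9.1 default. If intervals for each arm's proportion are also intended, say so and name their method. The cut-off of 10 can stay as a display rule.

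The change is one sentence, and the method is already planned for both endpoints, so little new programming is needed. The drawback is wider, somewhat conservative intervals in sparse subgroups: 97.6% coverage at 10 per arm at plan rates, and up to 99.8% at the lowest assumed rates. In the nine cases tabulated, coverage is never below 95.5%, and the interval never has zero width.

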10.0 Safety Analyses

10.1 General Considerations

The safety measurements will include AEs; vital signs (blood pressure and heart rate); mesopic and photopic, high-contrast, binocular CDVA; IOP; slit lamp biomicroscopy; manifest refraction; dilated fundoscopic examination; post-dose tolerability (for subjects reporting specific ocular symptoms), drop comfort; and pregnancy test.

Safety data will be summarized using the Safety population based on the treatment actually received, regardless of the treatment randomized. A subject's actual treatment will be determined by the first dose of study drug.

AEs and findings from biomicroscopy and ophthalmoscopy examinations will be coded using the Medical Dictionary for Regulatory Activities (MedDRA), according to the version of the MedDRA coding dictionary used for the study at the time of database lock. The actual version of the MedDRA coding dictionary used will be noted in the tables/listings and in the clinical study report.

10.2 Adverse Events

AEs will be summarized and presented using primary MedDRA SOCs and PTs. Specific adverse events will be counted once for each subject for calculating percentages, unless stated otherwise. In addition, if the same adverse event occurs multiple times for a subject, the highest severity and level of relationship to investigational product will be reported.

10.2.1 Treatment-Emergent Adverse Events

An AE will be considered a treatment-emergent adverse event (TEAE) if the AE began or worsened (increased in severity or became serious) on or after the date of the first dose of study treatment. Events where the onset date is the same as the study treatment start date are assumed to be treatment emergent.

In general, the number and percentage of subjects experiencing TEAEs will be summarized overall, as well as by primary MedDRA SOC and PT. The SOCs will be presented in alphabetical order, and the PTs will be presented in decreasing frequency order on active study treatment within each SOC. The number and percentage of subjects experiencing TEAEs will also be summarized by PT regardless of the SOC. TEAEs by PT summaries will be presented in decreasing frequency order on active study treatment.

10.2.2 Adverse Event Overview

Adverse events will be classified into ocular AEs and non-ocular AEs. An ocular AE will be determined as indicated on the AE form of eCRF (marked "OD" and/or "OS" to the question of "what was the location of the adverse event?"), and thus are not limited to AEs with primary SOC of eye disorders.

An overview of AEs will be presented consisting of the number and percentage of subjects experiencing at least one event for each of the following AE categories:

- TEAEs
 - Ocular TEAEs
 - Nonocular TEAEs
- TEAEs with reasonable possibility of being related to study treatment according to the investigator
 - Ocular TEAEs with reasonable possibility of being related to study treatment according to the investigator
 - Nonocular TEAEs with reasonable possibility of being related to study treatment according to the investigator

- Severe TEAEs
- Serious TEAEs
 - Ocular serious TEAEs
 - Nonocular serious TEAEs
- TEAEs leading to withdrawal of study treatment
 - Ocular leading to withdrawal of study treatment
 - Nonocular leading to withdrawal of study treatment
- TEAEs leading to death
- Adverse events of special interest (AESIs) within the following 2 categories (AESIs will be based on the search criteria in Appendix B):
 - Headache AESIs
 - Visual disturbance AESIs
- All deaths
- COVID-19 Infection

